10.3.5. Adverse events of special interest

Not applicable

10.3.6. Clinical laboratory parameters and other abnormal assessments qualifying as AEs or SAEs

In the absence of a diagnosis, abnormal laboratory findings assessments (e.g. clinical chemistry, haematology, or other tests) or other abnormal results the Investigator considers clinically significant will be recorded as an AE or SAE, if they meet the definition of an AE or SAE (refer to the Sections 10.3.1 and 10.3.2).

The Investigator must exercise his or her medical and scientific judgement in deciding whether an abnormal laboratory finding, or other abnormal assessment is clinically significant.

All events of ALT $\geq 3 \times$ upper limit of normal (ULN) and bilirubin $\geq 2 \times$ ULN ($>35\%$ direct bilirubin) or ALT $\geq 3 \times$ ULN, which may indicate severe liver injury (possible Hy's Law), must be reported as an SAE.

10.3.7. Events or outcomes not qualifying as AEs or SAEs

10.3.7.1. Pregnancy

Female participants who become pregnant after the first study intervention dose must not receive subsequent doses of the study intervention but may continue other study procedures at the discretion of the Investigator.

While pregnancy itself is not considered an AE or SAE, any abnormal pregnancy outcome or complication or elective termination of a pregnancy for medical reasons will be recorded and reported as an SAE. Please refer to the Section [10.3.2](#) for definition of SAE.

10.3.8. Recording and follow-up of AEs, SAEs, and pregnancies

The participants will be instructed to contact the Investigator immediately should they experience any signs or symptoms they perceive as serious.

When an AE/SAE occurs, it is the Investigator's responsibility to review all documentation (e.g., hospital progress notes, laboratory, and diagnostics reports) related to the event. This includes the assessment of COVID-19 cases as per the WHO definition [[WHO, 2022](#)]. The Investigator will then record all relevant information regarding an AE/SAE on the eCRF. The Investigator may not send photocopies of the participant's medical records to GSK instead of appropriately completing the eCRF.

There may be instances when copies of medical records for certain cases are requested by GSK. In this case, all participant identifiers will be blinded on copies of the medical records prior to submission to GSK.

The Investigator will attempt to establish a diagnosis pertaining to the event, based on signs, symptoms, and/or other clinical information. In such cases, the diagnosis should be documented as the AE/SAE instead of individual signs/symptoms.

A pDiary, hereafter referred to as Participant Diary, will be used in this study to capture solicited administration-site or systemic events. The participant should be trained on how and when to complete the Participant Diary.

Anyone who measures administration-site or systemic events and who will record the event in the Participant Diary should be trained on using the Diary. This training must be documented in the participant's source record. If any individual other than the participant is making entries in the Participant Diary, their identity must be documented in the Participant Diary/participant's source record.

The Investigator or delegate will transcribe the required information into the eCRF in English.

10.3.8.1. Time period for collecting and recording AEs, SAEs, and pregnancies

All AEs that occur during the 28 days following administration of each dose of study intervention (Day 1 to Day 28 and Day 169 to Day 196) must be recorded onto the appropriate section of the eCRF, irrespective of their intensity or whether they are considered related to the study intervention.

All SAEs and pregnancies will be collected as specified in [Table 12](#) and Section [10.3.10](#).

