3. OBJECTIVES AND ENDPOINTS

Table 3 Study objectives and endpoints (Amended, 21 August 2023)

Objectives	Endpoints
	Primary
Evaluate the safety profile of the Vi-CRM ₁₉₇ +O:2-CRM ₁₉₇ vaccine, with and without adjuvant.	
 • Percentage of participants with solicited administration-site events during 7 days after each vaccination, on the days of vaccination and the 6 subsequent days (study intervention administered on Day 1 and Day 169), per study group. • Percentage of participants with solicited systemic events during 7 days after each vaccination, on the days of vaccination and the 6 subsequent days (study intervention administered on Day 1 and Day 169), per study group. • Percentage of participants with unsolicited adverse events (AE) during 28 days after each vaccination, on the days of vaccination and 27 subsequent days (study intervention administered on Day 1 and Day 169), per study group. • Percentage of participants with any serious adverse event (SAE) from first vaccination until 28 days after second study intervention administration (Day 1 to Day 197), per study group. • Percentage of participants with AEs/SAEs leading to withdrawal from the study or withholding further study intervention administration, from first study intervention administration until 28 days after second study intervention administration (Day 1 to Day 197), per study group. • Percentage of participants with deviations from normal or baseline[†] values of haematological, renal, and hepatic panel test results at 7 days after each vaccination (Day 8 and Day 176), per study group.
	Secondary
Evaluate the long-term safety profile of the Vi-CRM ₁₉₇ +O:2-CRM ₁₉₇ vaccine, with and without adjuvant.	
 • Percentage of participants with any SAE from 28 days after second vaccination (Day 197) up to Day 337, per study group. • Percentage of participants with AEs/SAEs leading to withdrawal from the study from 28 days after second vaccination (Day 197) up to Day 337, per study group.

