4.2.2. Rationale for choice of follow-up period

No adverse events of special interest are planned to be collected in this study; the investigational vaccine does not contain any novel adjuvant and the Vi-CRM₁₉₇ component is already registered in India with no particular safety concern observed during its development (refer to the IB). No particular safety concerns have been identified in other licensed Vi-based vaccines against typhoid fever.

A 6-month follow-up period after the first study intervention administration will allow the identification of any possible late-occurring AEs. A follow-up of 28 days after the second study intervention administration will allow collection of unsolicited AEs and any other event as indicated in [Table 12](#). An extended 6-month safety follow-up after the second study intervention administration will collect any late-occurring SAE and AEs/SAEs leading to withdrawal or study discontinuation.

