5.2.1. Medical conditions

- Progressive, unstable, or uncontrolled clinical conditions.
- History of any reaction or hypersensitivity likely to be exacerbated by any component of the vaccine.
- Hypersensitivity, including allergy, to medicinal products or medical equipment whose use is foreseen in this study.
- Clinical conditions representing a contraindication to intramuscular vaccination and blood draws.
- Any confirmed or suspected immunosuppressive or immunodeficient condition, based on medical history and physical examination (no laboratory testing required).
- Any behavioural or cognitive impairment or psychiatric disease that, in the opinion of the Investigator, may interfere with the participant's ability to participate in the study.
- Acute* or chronic illness, clinically significant pulmonary, cardiovascular, hepatic, or renal functional abnormality, as determined by physical examination or laboratory screening tests.

*Participants with a minor illness (such as mild diarrhoea or mild upper respiratory infection) without fever may be enrolled at the discretion of the Investigator.

- Any clinically significant* haematological (haemoglobin level, white blood cell, lymphocyte, neutrophil, eosinophil, platelet, red blood cell count and erythrocyte mean corpuscular volume) and/or biochemical (alanine aminotransferase [ALT], aspartate aminotransferase [AST], creatinine, and total protein) laboratory abnormality.
- *The Investigator should use his/her clinical judgement to decide which abnormalities are clinically significant.
- Confirmed positive COVID-19 test during the period starting 14 days before the first administration of study vaccines (Day -14 to Day 1).
- Any other clinical condition that, in the opinion of the Investigator, might pose additional risk to the participant due to participation in the study.
- Confirmed or suspected autoimmune diseases (e.g., vitiligo, autoimmune thyroiditis).

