8.3. AEs, SAEs, and other safety reporting

8.3.1. Time period and frequency for collecting AE, SAE, and other safety information

Table 12 Timeframes for collecting and reporting of safety information

	SCR* D-21 to D-1	VAC 1 D1	D8	D29	VAC 2 D169	D176	D197	SFU D337
Administration-site and systemic solicited events		D1 to D7			D169 to D175			
Unsolicited AEs**		D1 to D28			D169 to D196			
AEs/SAEs leading to withdrawal from the study					D1 to D337			
SAEs**					D1 to D337			
SAEs related to the study intervention					D1 to D337			
SAEs related to study participation or concurrent GSK medication/ vaccine***					D-21 to D337			
Pregnancy					D1 to D197			
Any other event of interest for the study					D1 to D197			

*Consent obtained

**Unsolicited AEs/SAEs due to COVID-19 will be recorded according to the WHO case definition [WHO, 2022].

*** Any SAEs assessed as related to study participation (e.g., protocol-mandated procedures, invasive tests, or change in existing therapy) or related to a GSK product will be recorded from the time a participant consents to participate in the study.

D=Day; SFU=safety follow-up; SCR=Screening; VAC=Vaccination

The Investigator or designee will record and immediately report all SAEs in enrolled participants to the Sponsor or designee via the Expedited AE Reporting Form. Reporting should, under no circumstances, occur later than 24 hours after the Investigator becomes aware of an SAE, as indicated in Section 10.3.10. The Investigator will submit any updated SAE data to the Sponsor or designee within 24 hours of it being available. SAEs

related to study participation or to a concurrent GSK medication/vaccine will be collected from the time consent is obtained until the participant is discharged from the study.

During the extended safety follow-up period (Day 197 to Day 337), participants will be encouraged to inform the Investigator in a timely manner if they have any event meeting the description of an SAE. Any SAE reported during this period will qualify for expedited reporting according to Section 10.3.10. Any SAEs discovered retrospectively during the safety phone call on Day 337 will also be reported accordingly.

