9.4. Statistical analyses

9.4.1. Primary endpoint(s) (Amended, 21 August 2023)

[figure not shown]
Endpoint description	Analysis set	Statistical analysis methods
• Percentage of participants with solicited administration-site events during 7 days after each vaccination, on the days of vaccination and the 6 subsequent days (study intervention administered on Day 1 and Day 169), per study group	Solicited Safety Set	• Number and percentages of participants with at least one, any, and Grade 3 administration-site solicited AEs
• Percentage of participants with solicited systemic events during 7 days after each vaccination, on the days of vaccination and the 6 subsequent days (study intervention administered on Day 1 and Day 169), per study group	Solicited Safety Set	• Number and percentages of participants with at least one, any, and Grade 3 systemic solicited AEs
• Percentage of participants with unsolicited AEs during 28 days after each vaccination, on the days of vaccination and 27 subsequent days (study intervention administered on Day 1 and Day 169), per study group	Unsolicited Safety Set	• Number and percentages of participants with unsolicited AEs
• Percentage of participants with any SAEs from first vaccination until 28 days after second study intervention administration (Day 1 to Day 197), per study group	Exposed Set	• Number and percentages of participants with SAEs
• Percentage of participants with AEs leading to withdrawal from the study or withholding further study intervention administration, from first study intervention administration until 28 days after second study intervention administration (Day 1 to Day 197), per study group	Exposed Set	• Number and percentage of participants with AEs/SAEs leading to withdrawal from the study or withholding further study intervention administration
• Percentage of participants with deviations from normal or baseline t values of haematological, renal, and hepatic panel test results at 7 days after each vaccination Day 8 and Day 176 per study group*	Exposed Set	• Number and percentages of participants having haematological, renal, and hepatic abnormalities

[†]Baseline for post-first vaccination at Day 8 is Day 1 (can also be screening blood draw, if performed within 3 days of first vaccination), and baseline for post-second vaccination at Day 176 is Day 169.

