16.1.1. ADVERSE EVENTS LEADING TO DISCONTINUATION FROM STUDY OR FROM TREATMENT

Adverse events leading to permanent discontinuation from study and leading to discontinuation of study vaccine but continued further study procedures (safety or immunogenicity) will be identified by using the variable pertaining to outcome the Adverse Events page of the (e)CRF, and listed, separately. AEs leading to discontinuation from treatment will be listed.

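### A non-serious AE starting on Day 29 to Day 168 that stops dose 2 in a participant who stays in the study need not reach the AE page that the SAP reads, so a primary safety endpoint may be under-counted

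*Protocol*

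**What the plan says.** **The endpoint.** Protocol Section 3 (Table 3) lists as primary: "Percentage of participants with AEs/SAEs leading to withdrawal from the study or withholding further study intervention administration", over Day 1 to Day 197. Section 9.4.1 assigns it to the Exposed Set and plans to report "Number and percentage of participants with AEs/SAEs leading to withdrawal from the study or withholding further study intervention administration".

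**The collection rules.** Section 10.3.8.1 requires recording of "All AEs that occur during the 28 days following administration of each dose of study intervention (Day 1 to Day 28", with Day 169 to Day 196 as the second window. Table 12 (Section 8.3.1) gives the same two windows for unsolicited AEs. Its rows that run from D1 to D337 cover SAEs and "AEs/SAEs leading to withdrawal from the study". No row names AEs that lead to a withheld dose. The matching row of the Schedule of Activities (SoA) speaks of withdrawal without saying from what.

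**The other eCRF routes.** Section 7.1 treats stopping study intervention as separate from leaving the study (Section 7.2). It requires the primary reason on the eCRF, and a non-serious unsolicited AE is one of the listed reasons. Section 7.1.1 requires the criteria for stopping to be recorded as well. Neither rule has a date limit.

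**The analysis source.** SAP 16.1.1 says that AEs leading to discontinuation, including those in participants who stop vaccine but continue other procedures, "will be identified by using the variable pertaining to outcome the Adverse Events page of the (e)CRF". It then provides for listings.

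**The rationale.** Protocol Section 4.2.2 states: "A 6-month follow-up period after the first study intervention administration will allow the identification of any possible late-occurring AEs".

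**The concern.** The endpoint has two limbs. The study-withdrawal limb has a collection row that runs without a break. The withholding limb has none, although its window ("withholding further study intervention administration, from first study intervention administration until 28 days after second study intervention administration (Day 1 to Day 197") is just as continuous. Each participant is planned to receive two doses and enters the Exposed Set on receiving the first, so only dose 2 can be withheld. The events that define this limb must start before dose 2, and most of that time lies outside the general AE windows.

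An example makes the gap concrete. Section 5.2.1 lists "Confirmed or suspected autoimmune diseases (e.g., vitiligo, autoimmune thyroiditis" among its conditions, and Section 7.1.1 applies the 5.2.1 criteria to dose 2. Suppose such a condition is diagnosed on Day 80, is not serious, and the participant stays in follow-up. Under the protocol's own rules dose 2 is not given, and the case belongs in the primary endpoint. The event is outside Day 1 to Day 28, is not an SAE and did not cause study withdrawal, so neither Table 12 nor 10.3.8.1 expressly calls for an AE-page entry.

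At stake is a primary safety percentage in a first-in-human study. It could omit late-onset conditions that stop re-dosing, while the same eCRF holds the reason in another field.

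**Working it through.** The plan states no figure for this point, so the check is a comparison of windows and data sources, followed by arithmetic on days and denominators.

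**1. Which rule catches the Day 80 example?**

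| Source | Window | Requires an AE-page entry? |
|---|---|---|
| Unsolicited AEs (Table 12, 10.3.8.1) | D1–28, D169–196 | No, out of window |
| SAEs (Table 12) | D1–337 | No, not serious |
| AEs leading to study withdrawal (Table 12) | D1–337 | No, participant stays |
| SoA withdrawal row | includes the Day 29 and Day 169 visits | Unclear, term not qualified |
| Other events of interest (Table 12) | D1–197 | Unclear, not defined |
| Discontinuation reason and criteria (7.1, 7.1.1) | no limit | Recorded in the eCRF, but no AE entry stipulated |

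SAP 16.1.1 names the AE page and none of the other fields.

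**2. Length of the gap.** Dose 1 is Day 1 and planned dose 2 is Day 169.
- Day 29 to Day 168 inclusive: 168 − 29 + 1 = 140 days.
- Share of the time before dose 2: 140/168 = 83.3%. Share of the endpoint window: 140/197 = 71.1%.
- Allowed dose interval of 158 to 178 days (Table 2): the gap is 158 − 28 = 130 to 178 − 28 = 150 days, or 82.3% to 84.3% of the time before dose 2.
- Special-circumstances interval of 154 to 182 days (Table 6): 126 to 154 days, or 81.8% to 84.6%.

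**3. Weight of one participant.** 1/24 = 4.2 percentage points in a full-dose arm; 1/12 = 8.3 points in a low-dose arm.

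**4. Illustration of lost sensitivity.** The chance of seeing at least one event is 1 − (1 − p)^n. This reproduces protocol Table 14: n = 24 and p = 5% give 70.8%; n = 24 and p = 1% give 21.4%; n = 12 and p = 5% give 46.0%.

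The documents give neither a rate for these AEs nor the share s that would reach the AE page, so both are assumptions. Replacing p by p × s:

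| n | p | s = 28/168 | s = 0.5 | s = 0.75 | s = 1 |
|---|---|---|---|---|---|
| 24 | 5% | 18.2% | 45.5% | 60.0% | 70.8% |
| 24 | 1% | 3.9% | 11.3% | 16.5% | 21.4% |
| 12 | 5% | 9.6% | 26.2% | 36.8% | 46.0% |

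The first column is a worst case. It assumes that onset is uniform before dose 2 and that only Day 1 to Day 28 onsets reach the AE page. The last column is the case with no loss.

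**The case against.** A reader might infer that these AEs are not collected at all unless the participant leaves the study, and that the endpoint is therefore under-counted. The documents do not support that.

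- Sections 7.1 and 7.1.1 require the reason and criteria for stopping vaccine in the eCRF, whether or not the participant stays.
- Section 9.3.1.1 requires certain intercurrent conditions to be recorded, and the SoA marks this at the Day 29 and Day 169 visits. Subject to the investigator's judgement, this could include the example above.
- Section 6.8 records medication associated with an AE from Day 1 to Day 197.
- Section 8.2 makes investigators responsible for following up AEs that caused withdrawal from the study intervention, so the intent to track them is visible.
- The SoA row can be read to cover both kinds of withdrawal, and the undefined Table 12 row for other events of interest has exactly the endpoint's window.
- SAP 16.1.1 plainly expects these events on the AE page. The eCRF is not available for review, so its actual content cannot be checked.
- SAP Section 9 plans a listing of treatment discontinuations.

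All of this stands, and it turns a claim of certain loss into one of possible loss. It does not close the gap. A reason category is not an AE entry with term, onset, grade and causality. The intercurrent-condition record is defined for per-protocol elimination. An undefined row cannot be relied on to carry a primary endpoint. A listing of discontinuations does not feed the endpoint's numerator.

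Two further inferences should be resisted. The 83.3% is a share of days, not of events: withholding may follow an AE that began on Day 1 to Day 28, when all AEs are recorded. And the sentence in Section 4.2.2 explains the length of follow-up; it is not a recording rule, so it is loose wording and not a firm contradiction.

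**Conclusion.** The mismatch is real but narrow. The stated collection rules do not expressly require an AE-page record of a non-serious AE with onset on Day 29 to Day 168 that leads to withholding dose 2 in a participant who remains in the study. The SAP names that page as its only source for such events. A site and a programmer who each follow their document to the letter could leave the event out of the primary endpoint.

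The direction of any error is downward. Its size cannot be estimated, because no rate for such events is given. The conclusion rests on reading the continuous Table 12 row as it is worded (study withdrawal) and on the eCRF having no further rule that forces an AE entry.

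A related inconsistency is that protocol 9.4.1 plans a number and percentage, while SAP 16.1.1 provides only for listings and SAP 3.3 declares no changes from the protocol. The table templates were not available, so they may already contain the count.

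The point is worth correcting before the endpoint is analysed, but it does not undermine the study. All analyses are descriptive, SAEs are collected without a gap, and holding rules 1a–1d are monitored continuously.

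**What to change.** **Protocol.** In Table 12, the SoA row and Section 10.3.8.1, add AEs/SAEs leading to withholding of further study intervention, recorded on the AE page whatever the onset day, from D1 to D197. Keep D1 to D337 for AEs/SAEs leading to study withdrawal. The longer window is not needed for withholding, because the endpoint ends on Day 197 and no dose follows the second. It would also help to name in Section 4.2.2 the event types actually collected between Day 29 and Day 168.

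**SAP 16.1.1.** Derive the endpoint from the Section 7.1 discontinuation-reason field as well as the AE page, reconcile the two sources, and report the number and percentage by group planned in protocol 9.4.1, not only listings.

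**Cost.** Wording in a few protocol places and one SAP derivation. The Day 169 visit already includes the check of contraindications, and Section 7.1 already requires the reason to be recorded, so no new visit or procedure is needed. The downside is a few extra AE entries and one reconciliation check. If the protocol is not amended again, the SAP change alone would bring into the count the cases that the reason field attributes to an AE, though without the onset, grade and causality detail of an AE entry.

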10.3.8.2. Follow-up of AEs, SAEs, pregnancies, or any other events of interest

After the initial AE/SAE/pregnancy or any other event of interest, the Investigator is required to proactively follow each participant at subsequent visits/contacts. All SAEs will be followed up until the event is resolved, stabilised, otherwise explained, or the participant is lost to follow-up.

Other non-serious AEs must be followed until resolution or until the participant is lost to follow-up.

